# Figure 2 Multiplicity adjustment within study for approach

#### For Countries outside the US:

To increase the probability to detect a potential treatment effect on the key secondary endpoints, some of which are rare but clinically important events, they will be analyzed using the pooled data from the two studies (GLPG1690-CL-303 and GLPG1690-CL-304). The confirmatory testing on these secondary endpoints will be done only if the primary endpoints in both studies show significance and a step-down closed-testing multiplicity adjustment will be applied, as shown in Figure 3. A key secondary endpoint in the pooled analysis will only be tested for a dose if the higher order endpoint also showed significant for that dose. This analysis will be presented in the Section 2.7.3 Summary of Clinical Efficacy (and Module 5 Integrated Summary of Efficacy). Details of the pooled analyses will be provided in the pooled-analysis SAP.

Results for the key secondary endpoints for each individual study will be summarized within its CSR and will enable the evaluation of consistency of the results between the studies. An overview of the multiplicity adjustment for the primary and key secondary endpoints is provided in Figure 3.

Figure 3 Multiplicity adjustment within study for Countries outside the US

# 9.3.2. Spirometry Parameters

All spirometry evaluations should be performed pre-bronchodilator. Spirometry data taken postbronchodilator will be excluded from the analysis.

The clinical study center-based spirometry must meet the criteria for acceptability and repeatability as defined in the American Thoracic Society / European Respiratory Society / Japanese Respiratory Society / Latin American Thoracic Association (ATS/ERS/JRS/ALAT) guidelines (Miller, et al., 2005) for screening, and will be based on ATS/ERS/JRS/ALAT guidelines after randomization.

Pulmonary function will be measured in a standardized manner and results should be transmitted electronically during the visit immediately after performing the spirometry and evaluated by a central reader. In case the acceptability and repeatability criteria as specified by ATS/ERS/JRS/ALAT guidelines are not met, a repeat spirometry should be performed during the same visit of the screening period. After randomization, a repeat spirometry should be performed during the same visit, based on the ATS/ERS/JRS/ALAT guidelines.

The data will be coded as "acceptable", "borderline acceptable" and "unacceptable", "unacceptable" values will be excluded from analyses.

The following parameters will be measured or calculated as part of the spirometry assessment:

- FVC (mL)
- Percent predicted FVC (%), as available in the database
- FEV1 (L) and percent predicted  $FEV_1(\%)$
- FEV1/FVC ratio
- FEF25-75 (mL/s).

The '2012 Global Lung Function Initiative Equations' will be used to calculate the predicted values (Ratitch B, 2013).

The spirometry endpoints will be analyzed using the FAS, including all available data before lung transplant for subjects who took at least one dose of IP, and excluding values post-bronchodilator.

For each of the spirometry parameters, descriptive statistics will be provided for the values, changes and percent change from baseline per time point up to the end of the study and per treatment group. Results will also be graphically displayed by means of line plots of the mean (SE) over time-by-treatment group.

A similar summary table and graph will also be provided by stratification factor (standard of care) and reason for not being on SOC.

# 9.3.2.1. Primary Endpoint: Rate of Decline in FVC over a Period of 52 Weeks

The primary endpoint of annual rate of decline in FVC at Week 52 (in mL) will be analyzed, including data up to and including the 52-week analysis window defined in Section 6.3. A random coefficient regression model (linear slope model) will be used including sex, age, height and stratification factor as covariates and a random intercept and slope. The treatment effect is determined by using estimated slopes for each treatment group on the basis of the time-by-treatment interaction term from the mixed model. All available FVC values (as defined by the analysis windows) from baseline to Week 52 will be used including FVC measurements at the follow-up visit for subjects who discontinue IP prematurely and do not complete the study visits through Week 52. The model will be fit using the SAS PROC MIXED procedure, details are in Appendix 1.

The assumptions of the model will be investigated.

The same model will be used for the pooled analysis for the integrated summary of efficacy adjusted for study. More detail will be in a separate SAP.

A similar analysis will also be provided by stratification factor (standard of care).

The percent predicted FVC will be analyzed using a similar random coefficient regression model (linear slope model) as FVC expressed in mL.

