4.6. Measures to Minimize Bias

4.6.1. Randomization

At screening, subjects will be assigned a subject identification number. When a subject is confirmed to be eligible for the clinical study, he/she will be randomized.

A total of approximately 750 subjects will be randomized in a 1:1:1 ratio to receive GLPG1690 600 mg q.d., GLPG1690 200 mg q.d., or matching placebo for at least 52 weeks. Allocation of each subject to a given treatment will be described in a randomization list prepared by a CRO. This randomization list will be stratified in a balanced manner for background local standard of care for treatment of IPF (nintedanib, pirfenidone, or neither). Recruitment may stop earlier in one or more strata to maintain the balance as indicated, while the other strata(s) continue to recruit. Upon qualification for the study, allocation of each subject to a given treatment will be done using a centralized electronic system (interactive web response system [IWRS]) with permuted blocks.

For each subject at each visit, the clinical study center will contact the IWRS for the appropriate treatment number to be assigned. Each medication kit will contain the relevant IMP for the period until the next visit.

Subjects and study personnel will be blinded to the treatment assignment. Additional details on blinding and unblinding are provided in Section 4.6.2.

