7.1. Determination of Sample Size

To account for multiple testing due to multiple doses, a Bonferroni approach [9] will be applied to the alpha level with higher priority given to the high-dose group. The primary endpoint will be tested at a 4% level when comparing GLPG1690 600 mg to placebo and a 1% level for GLPG1690 200 mg group versus placebo.

Denoting Δ_{600} and Δ_{200} , the true treatment differences of the two GLPG1690 treatment groups with placebo, and assuming a common standard deviation (SD) on the 52 weeks decline in FVC of 275 mL, the probabilities that 0, 1, or 2 treatment comparisons with placebo are statistically significant, are presented in Table 2. The family-wise error rate is protected at 5% using the Bonferroni procedure. The so-called disjuncture power of the study is the probability that 1 or 2 hypotheses are rejected and is displayed in the right-most column of Table 2.

A meta-analysis of the seven placebo-controlled studies that have been conducted on nintedanib, pirfenidone, and pamrevlumab has revealed that the treatment effect at 52 weeks is estimated to be approximately 119 mL in a treatment-naïve population, the effect observed with nintedanib alone is similar (112 mL) [32]. Little information is available on the expected treatment effect of GLPG1690 in addition to pirfenidone or nintedanib. Table 2 gives an overview of the power for different scenarios for the overall treatment effect in the population of subjects on standard of care (either pirfenidone or nintedanib, or neither pirfenidone nor nintedanib).

Since the linear-slope model on the annual rate of decline in FVC accounts for missing data, the number of subjects randomized and the number of subjects included in the model is expected to be equal. An equal number of 250 subjects will be randomized to each treatment group to have at least 80% power to show a significant effect assuming the 600-mg group has a treatment effect of at least 80 mL in the overall population of treatment naïve and patients on standard of care.

Table 2: Probability of Statistical Significance of 0, 1, or 2 Treatment Comparisons With Placebo

mL	0 Successful	1 Successful	2 Successful	Power
$\Delta_{600}=80$ $\Delta_{200}=80$	6.8%	23.4%	69.9%	93.2%
$\Delta_{600}=80$ $\Delta_{200}=60$	10.1%	46.9%	43.0%	89.9%
$\Delta_{600}=80$ $\Delta_{200}=20$	11.5%	84.4%	4.1%	88.5%
$\Delta_{600}=80$ $\Delta_{200}=0$	11.2%	88.0%	0.7%	88.8%
$\Delta_{600}=90$ $\Delta_{200}=60$	5.1%	51.1%	43.8%	94.9%

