# 9.3.1. Level of Significance

Given no market authoristation applicaton for ziritaxestat for the treatment of IPF will be submitted anymore, no pooled analyses combining data from both studies will be performed and the below multiplicity adjustment strategy for countries outside US, does not apply. Only abbreviated CSRs per study will be written as explained earlier in this document.

Statistical tests will be done at a 2-sided level. For the analysis of the primary endpoint, to account for the multiple testing due to two doses being compared to placebo, a Bonferroni approach (Hochberg, 1988) will be used with higher priority given to the high-dose group. The primary endpoint will be tested at a 4% level when comparing GLPG1690 600 mg to placebo and a 1% level for GLPG1690 200 mg group versus placebo.

With respect to the multiplicity adjustment for the key secondary endpoints an additional approach was requested by the compared to European Union (EU) countries. For countries outside US and EU, the EU approach will be applied.

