# 11. APPENDICES

## 1. ADDITIONAL DETAILS ON PRIMARY ANALYSIS

For both parameters (FVC [in mL] or percent predicted FVC, separately), the annual rate of decline will be analyzed using a random coefficient regression model (linear slope model) including sex, age, height and stratification factor (stratum: pirfenidone, nintedanib and neither) as covariates and a random intercept and slope. The treatment effect is determined by using estimated slopes for each treatment group on the basis of the time-by-treatment interaction term from the mixed model. All available FVC values, as defined by the analysis windows will be used, including FVC measurements at the follow-up visit for subjects who discontinue the IP prematurely and do not complete the study visits. The model will be fit using the SAS Proc Mixed procedure, details are below. The assumptions of the model will be investigated.

In the primary analysis only data up to the Week 52 will be used, before a lung transplant. In a secondary analysis all data will be used up to the end of the study, before a lung transplant.

The statistical model can be written as follows:

$$\begin{split} Y_{itk} = (\alpha + a_i) + (\gamma + \beta_{T1}T_{k1} + \beta_{T2}T_{k2} + g_i)t + \beta_g \text{ Gender} + \beta_a \text{ age} + \beta_h \text{ Height} + \beta_{sP} \text{ Stratum } (P) + \beta_{sN} \text{ Stratum } (N) + \epsilon_{it} \end{split}$$

Where  $Y_{itk}$  is the FVC value for the ith subject at time t in treatment group k,  $T_{k1}=0$  for placebo and  $T_{k1}=1$  for GLPG1690 200 mg,  $T_{k2}=0$  for placebo and  $T_{k2}=1$  for GLPG1690 600 mg,  $\beta_{T1}$ ,  $\beta_{T2}$  are the effects of GLPG1690 on the slope.

 $\alpha$  and  $\gamma$  are the fixed effects for the intercept and slope, respectively

 $a_i$  and  $g_i$  are random effects for the intercept and slope for subject i, these are assumed to be normally distributed with mean 0 and unstructured variance-covariance matrix.

 $\beta_g$ ,  $\beta_a$ ,  $\beta_{sP}$ ,  $\beta_{sN}$  and  $\beta_h$  are subject specific demographic coefficients for gender, age, stratification factor (standard of care) and height at baseline.

 $\varepsilon_{it}$  is the random error for subject i at time t, assumed to be normally distributed with mean 0 and variance  $\sigma_{\varepsilon}^2$ .

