An unstructured variance-covariance matrix will be used to model the variance-covariances for the random slope, random intercept. The variance-covariance matrix for the error terms is assumed to have a variance-component structure.

If this model fails to converge, other structures will be tested for the variance-covariance matrix for the error terms (e.g. heterogeneous Toeplitz). Depending on the structure used, the random slope and random intercept may need to be dropped from the model. The structure with the best fit, based on Akaike's information criterion, will then be used.

The linearity assumption of the model will be explored graphically be the lineplots over time of the observed FVC values (mL) as well as change from baseline and LS means at each time point.

The following SAS code is to be used:

proc SORT data = FVC ;

By subject visit;

run;

Proc MIXED data = FVC order = internal;

CLASS subject treatment visit gender stratum;

MODEL FVC = treatment \* time gender age height stratum / solution CL ddfm=KR ;

RANDOM intercept time / type=UN subject = subject ;

REPEATED visit / type= Simple subject = subject ;

ESTIMATE "GLPG 1690 600 mg qd - Placebo" treatment\*time -1 0 1 / e CL ;

ESTIMATE "GLPG 1690 200 mg qd - Placebo" treatment\*time -1 1 0 / e CL ;

run;

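### The primary slope model adjusts for standard of care on the FVC level only; a stratum-by-time term would recover a little precision at almost no cost

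*SAP*

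**What the plan says.** Protocol 4.6.1: "This randomization list will be stratified in a balanced manner for background local standard of care for treatment of IPF", with three levels (nintedanib, pirfenidone, neither).

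SAP 9.3.2.1 fits a random coefficient regression "including sex, age, height and stratification factor as covariates and a random intercept and slope". The treatment effect is taken from the time-by-treatment interaction. Protocol 7.3.4 describes the same model.

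SAP Appendix 1 makes the role of stratum explicit. In the equation, the only terms that multiply time are the common slope, the two dose effects and the subject's random slope. The stratum parameters stand outside that bracket and "are subject specific demographic coefficients for gender, age, stratification factor (standard of care) and height at baseline". The MODEL statement agrees: treatment*time is the only term involving time, followed by "gender age height stratum / solution CL ddfm=KR".

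Stratum also appears elsewhere. SAP 9.3.2.1 plans a similar analysis by stratum. SAP 9.3.10 keeps stratum as a subgroup with a treatment-by-subgroup term. The MMRM sensitivity analysis (9.3.2.2.1) includes stratum in a model for change from baseline.

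**The concern.** A main effect of stratum in a model for FVC values explains differences in how high FVC is. The tested parameter is how fast FVC falls. If subjects on nintedanib, pirfenidone and neither decline at different rates, that difference has nowhere to go in this model except the random-slope variance.

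Stratified allocation balances the strata across arms, so the between-stratum part of the slope variance does not add to the true sampling error of the treatment contrast. The model-based standard error still includes it. The reported interval is then wider than the design warrants, the test is slightly conservative, and a little power is given away.

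The documents make slope differences plausible. Protocol 7.1 cites treatment effects at 52 weeks of about 119 mL (meta-analysis) and 112 mL (nintedanib). Protocol 4.2 cites residual declines of 125 and 114 mL on nintedanib and about 200 mL on pirfenidone.

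**Working it through.** **Inputs from the documents.** There are 250 subjects per arm, an SD of 275 mL and an effect of 80 mL (Protocol 7.1). The 600 mg dose is "tested at a 4% level when comparing GLPG1690 600 mg to placebo" (z = 2.054), and the level is a "1% level for GLPG1690 200 mg group versus placebo" (z = 2.576). "Statistical tests will be done at a 2-sided level" (SAP 9.3.1).

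**Reproducing the plan's figure.** SE = 275 × √(2/250) = 24.60 mL. Power for 600 mg alone = Φ(80/24.60 − 2.054) = 88.5%. With two z-statistics correlated 0.5 through the shared placebo arm, the 80/0 row of Table 2 gives 88.8% (stated 88.8%), the 80/80 row 93.4% (stated 93.2%) and the null row 4.8% (stated 4.8%). The plan's own calculation holds.

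**Assumptions.** Three inputs are not in the documents:
- The share of subjects on neither drug: 20%, one third or 50%.
- The slope gap: 112 or 119 mL/year between neither and treated subjects. The alternative is 120/200/232 mL for nintedanib/pirfenidone/neither, where 232 = 120 + 112.
- The 275 mL is taken as the overall SD across strata.

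**Formulas.**
- Between-stratum variance for a two-level gap: B = p(1 − p)d².
- Reported SE without the term: √(2 × 275²/250) = 24.60 mL.
- True SE under stratified allocation: √(2 × (275² − B)/250).
- Power without the term: Φ((80 − z × SE reported)/SE true).
- Power with the term: Φ(80/SE true − z).
- Actual size without the term: 2Φ(−z × SE reported/SE true).

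**Worked case, d = 112 and p = 1/3.** B = (1/3)(2/3)(112²) = 2,787.6, which is 3.69% of 75,625. True SE = √(2 × 72,837.4/250) = 24.14 mL. Power for 600 mg without the term = Φ((80 − 2.054 × 24.60)/24.14) = 88.9%; with it, Φ(80/24.14 − 2.054) = 89.6%. Size without the term = 3.64%.

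| Gap (mL/year) | Share on neither | B as % of 275² | True SE (mL) | Reported SE too wide by | 600 mg power, without → with | 200 mg power, without → with | Actual size at 4% |
|---|---|---|---|---|---|---|---|
| 112 | 20% | 2.65 | 24.27 | 1.35% | 88.8 → 89.3% | 75.4 → 76.4% | 3.74% |
| 112 | 1/3 | 3.69 | 24.14 | 1.90% | 88.9 → 89.6% | 75.5 → 77.0% | 3.64% |
| 119 | 1/3 | 4.16 | 24.08 | 2.15% | 89.0 → 89.8% | 75.5 → 77.2% | 3.59% |
| 119 | 50% | 4.68 | 24.01 | 2.43% | 89.0 → 89.9% | 75.6 → 77.5% | 3.54% |
| 120/200/232 | 1/3 each | 2.93 | 24.23 | 1.50% | 88.8 → 89.4% | 75.4 → 76.6% | 3.71% |

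With no gap, the rows without and with the term are identical.

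**If 275 mL is instead the within-stratum SD.** Power for 600 mg without the term is 87.9% (112 mL, 20%) down to 87.5% (119 mL, 50%: Φ((80 − 2.054 × 25.17)/24.60), where 25.17 = 24.60 × √1.0468). With the term it is 88.5%.

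**Simulation of the Appendix 1 model.** This used 750 subjects, 10 visits, complete data, a 112 mL gap, and assumed residual SD 130 mL, intercept SD 600 mL and intercept–slope correlation 0.2. The model SE was 24.3 mL without the term and 23.9 mL with it. Power was 89.8% and 90.5% (4,000 runs). Type I error was 3.95% and 4.3% (6,000 runs; the Monte Carlo standard error at 4% is √(0.04 × 0.96/6000) = 0.25 points). The estimate was unbiased.

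**How large a gap would matter.** With one third on neither drug, the 600 mg loss passes 2 points only at a gap of about 195 mL.

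**The case against.** The size rests on inputs that the documents do not supply. The 112 and 119 mL figures are effects against placebo in other trials, not differences between these strata. Subjects in the neither stratum are there for any reason (Protocol 4.1) and were not randomised to it. Treated subjects have already had at least two months on a stable dose. Standard of care may change during the study while the analysis stratum stays fixed (SAP 7.6), which would dilute any gap. All of this stands, so the gap is an assumption and the loss could be nil.

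The protocol, SAP text, equation and code are consistent with each other, and intercept-only covariates are a legitimate choice. That also stands: this is an efficiency point, not an error.

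Stronger readings are tempting, and the documents do not support them:
- *The comparison ignores the stratified randomisation.* It does not. Stratum is in the model, balance by stratum still lowers the true variance of the contrast, and by-stratum analyses are planned. Those analyses do not, however, change the standard error of the primary test.
- *The gain is 0.8–1.5 points.* A reader gets this by setting 89.3–89.9% against 88.5%. The 88.5% treats the inflated SE as the true sampling error and so credits the model term with a gain that the stratified design already delivers.
- *The trial is underpowered or the test invalid.* Power for 600 mg stays above 80% in every scenario above, and the size error is on the conservative side.
- *The contrast is biased.* Bias could arise if discontinuation differed by arm within stratum, but the documents give no such rates. With complete data there is none.

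Finally, SAP version 2.0 was written after the studies were halted and part of the team unblinded (SAP 2.7). That affects how a change is made and documented, not whether the term is sensible.

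**Conclusion.** The point holds as a minor efficiency matter. The primary model adjusts for the stratification factor on a quantity that is not tested and leaves it off the one that is. On the assumed gaps and shares, the reported SE is 1.35–2.43% too wide, actual size is about 3.5–3.7% against 4%, and power at 80 mL is lower by about 0.5–0.9 points for 600 mg and about 1–2 points for 200 mg. These figures depend on slope gaps borrowed from separate cited studies, on assumed stratum shares, and on reading 275 mL as the overall SD. If slopes do not differ by stratum, there is no loss.

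**What to change.** Add stratum*time (2 df) to the Appendix 1 equation and MODEL statement, so that the fixed effects read treatment*time, stratum, stratum*time, gender, age and height. Amend SAP 9.3.2.1 to match, along with the description carried over from Protocol 7.3.4. Keep the two treatment*time ESTIMATE contrasts as they are. Where slopes per arm are reported, state how they are averaged over strata. Use the same term for percent predicted FVC and for the slope model on all study data (9.3.2.2.5).

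Because part of the study team was unblinded before SAP version 2.0, either document the change as made after unblinding, with its reason, in the CSR as SAP 9.1 provides, or keep the prespecified model as primary and report the stratum*time model beside it as supportive.

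The cost is one model term and a sentence of text. It needs no new data, leaves the estimand unchanged because the model is linear, and loses essentially nothing if the strata share a slope.

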# 9.3.2.2. Sensitivity Analyses to the Primary Analyses

Since no treatment effect was observed and the study was stopped for lack of efficacy, sensitivity analyses to investigate the robustness of results will be limited. Description of sensitivity analyses are kept as documented in the original SAP for reference, analyses that will not be performed are in italic font.

Several sensitivity analyses are planned to investigate the impact of protocol violators, missing data, treatment discontinuation, and changes in standard of care. If during the blinded review of

Galapagos

the data more sensitivity analyses are deemed necessary these will be added to this SAP before unblinding for the final analysis of the CSR.

For the below sensitivity analyses and per dose group (600 mg, 200 mg) the estimate, 95% CI of the treatment effect compared to placebo will be presented on the same forest plot together with those of the primary analysis.

# 9.3.2.2.1. Sensitivity Analysis not Assuming a Linear Trend over Time

A mixed-effects model for repeated measures (MMRM) with treatment, time (as a categorical factor defined by the analysis windows in Section 6.3), treatment\*time, stratum and baseline value as factors in the model will be applied to the change from baseline in FVC value in mL. Least squares (LS) means (with 95% CI) will be estimated from the model at each time point for each treatment group as well as the differences from placebo in LS means (and 95% CIs). Details on the model are in Appendix 3.

This approach provides another estimate (LS mean difference) for the primary estimand.

